2.3. Benefits and Risks

CCI

Pain:

The SK procedure can cause pain to the participant but is generally safe and well tolerated. Pain can be managed by the use of artificial tears or a bandage contact lens

Infection:

The SK procedure carries a risk of infection and requires prophylactic antibiotics. Infectious keratitis occurs in 2% of patients [Vo, 2015]. These data are from patients who underwent epithelial debridement and diamond burr polishing of the Bowman's membrane (n=91 eyes).

Delayed Healing:

In this study, it is anticipated that SK-induced epithelial defect will heal within 7 days with the use of a bandage contact lens.

Typically, healing occurs in 2 days for a 3–4 mm central epithelial debridement [Sta Iglesia, 2000] [Wilson, 2004] [Park, 2019]. Temporary scarring/subepithelial haze can occur in 21% of eyes at 1 month post procedure and in 9% of eyes at last follow-up and is not visually significant. No complications resulting in impaired vision at final follow-up have been reported [Vo, 2015] [Murueta-Goyena, 2018].

Comorbidities such as diabetes and dry eye can significantly delay the healing process and may require adjuvant therapy (e.g., bandage contact lens).

2.3.1. Benefit Assessment

In participants with central corneal deposits, the SK procedure may or may not be therapeutic. Any improvement in visual acuity will be documented via a Snellen eye test pre- and post-procedure as detailed in the SoA. Although this procedure is being performed primarily for diagnostic purposes, an improvement in vision, at least

temporarily, is a potential benefit. For any given patient it is not possible to predict whether an improvement in vision will occur or not.

2.3.2. Overall Benefit/Risk Conclusion

Approaches to minimize risk include supportive care with the performance of the SK, utilization of a post-procedure bandage contact lens along with topical antibiotics and a steroid, and close monitoring.

The scientific data that will be obtained from this study will provide critical information on the pathologic nature of the corneal epithelial changes, which may inform potential mitigating treatments for participants suffering from corneal symptoms while receiving treatment for RRMM with belantamab mafodotin.

3. OBJECTIVES AND ENDPOINTS

Objectives	Endpoints
Primary: To characterize corneal epitheliopathy in participants treated with belantamab mafodotin	Primary: Pathologic characteristics and composition of corneal epithelial changes obtained by impression cytology (IC) or SK in participants treated with belantamab mafodotin
Secondary: 
• To correlate clinical data, including visual acuity and symptoms, as well as grade and appearance of corneal changes on imaging, with histopathologic findings• Safety profile of the impression cytology or SK procedure	Secondary: 
• Results of analysis of clinical/imaging data with histopathologic findings• AEs associated with the impression cytology or SK procedure

CCI

4. STUDY DESIGN

4.1. Overall Design

- This study is available to any participant who has received or is currently receiving belantamab mafodotin treatment through a clinical trial (including an ISS, or an access program) or a Physician prescription; they do not need to be on active treatment as long as they meet inclusion criteria specified below.
- Up to 25 participants will complete the procedure. Once a total of 5 participant samples from SK procedure has yielded evaluable material for pathologic examination and composition analysis of the corneal epithelial changes, further enrollment will cease.
- Each patient will have a total of 3 (IC) to 6 (SK) visits. Additional followup visits may be required in the event of delay in healing from the ocular procedures.
- One eye will be the study eye. The study eye will be the eye most affected with the corneal epithelial changes. If both eyes are equally affected, the poorer-seeing eye will be selected.
- Each participant will only have one corneal procedure (impression cytology or SK). All participants will be asked to participate in the ^{CCI} [REDACTED]
[REDACTED]

4.2. Study Procedures

- Corneal epithelial tissue will be obtained by IC or SK from the study eye showing the greater number of MECs. Removal of the limbal tissue should be avoided during the SK procedure, if possible. The sample material will be processed and transferred to the central laboratory.
- Assessments of the epithelial changes will be made, including but not limited to histology, electron microscopy, and immunohistochemistry. See table below for methods to investigate the corneal epithelium.
- Anterior segment slit-lamp photography of both eyes.
- Confocal microscopy, if available, in the study eye.
- ^{CCI} [REDACTED]

Name of analysis ^a	How should the sample be fixed/prepared?	Description of test	References
Microscopic evaluation/ histopathology	Tissue fixed in 10% neutral buffered formalin and embedded in paraffin. 5 µm sections examined microscopically	Histologic characterization – description of cells in the epithelium; will show apoptotic cells	[Lee , 2018] [Stiefel , 2019]
		Hematoxylin-eosin (H&E) stain: hematoxylin is used to illustrate nuclear detail (color is related to the amount of DNA); eosin is used to stain cytoplasm	[Sampias , 2019]
		Periodic acid-Schiff (PAS) stain: used for structures with a high proportion of carbohydrates (e.g., glycogen, glycoproteins, proteoglycans) typically found in connective tissues, mucus, and basement membranes	[Anderson , 2020]
		Congo red stain: used for amyloid epithelial changes	[Byrwa-Neff , 2020]
		Masson's trichome stain: used for collagenous connective tissue fibers; differentiates collagen and smooth muscle; used in the detection of diseases or changes in connective/muscle tissue	[Anderson , 2020]
Immunohisto-chemistry (IHC) for IgG	Tissue samples examined by IHC; performed with primary antibodies	Will identify IgG-positive intracytoplasmic granules in the epithelium; because belantamab mafodotin is an IgG1, it could show if belantamab mafodotin itself is deposited in the epithelium	[Lee , 2018] [Stiefel , 2019]
Electron microscopy	Samples for transmission electron microscopy will be processed using standard techniques: tissues will be epoxy embedded in standard fashion without post fixation. Ultrathin sections measuring 80 nm will be stained with uranyl acetate and lead citrate and examined in a Zeiss EM900 transmission electron microscope at 80 kV	Used for high-resolution images of detailed structures such as tissues, cells, organelles, and macromolecular complexes	[Electron Microscopy , 2020] [Stiefel , 2019]

Name of analysis ^a	How should the sample be fixed/prepared?	Description of test	References
Mass spectrometry (nanoscale liquid chromatography coupled to tandem mass spectrometry [nano LC-MS/MS])	For comprehensive methods, see [Karring, 2012]	Analysis of peptide mixtures in sample-limited situations Can be used to identify in-gel digested protein spots Has been utilized to determine the composition of corneal epithelial changes associated with mutations in TGFBI gene	[Karring, 2012] [Gaspari, 2011]

^aHistologic characterization, H&E, and PAS are required; all other stains and techniques are at the investigator's discretion.

Participants who receive belantamab mafodotin consistently display microcyst-like epithelial changes on slit-lamp examination and/or experience symptoms including changes in visual acuity, blurred vision, and dry eye, which are recognized AEs associated with MMAF-containing antibody therapies, including SGN-75 [Tannir, 2014], SGN-CD19A, and ABT-414 [Reardon, 2017], but the exact mechanism is unknown. The corneal findings by slit-lamp examination have been described in participants treated with high-dose cytarabine [Guthoff, 2010]. The specific corneal AE seen with belantamab mafodotin therapy has not been replicated in preclinical models, and confirmatory corneal histology is lacking to support and confirm the working explanatory theory for this corneal toxicity.

The mechanism of corneal events in participants treated with belantamab mafodotin is unknown, but it is likely related to MMAF uptake into the corneal basal epithelial stem cells that are located in the basal epithelial layer of the cornea [Donaghy, 2016]. These cells have mitotic activity, and, furthermore, daughter cells migrate anteriorly as they differentiate into wing cells and terminal superficial epithelial cells. Both processes are microtubule dependent and can be disrupted by potent tubulin inhibitors such as MMAF. The leading hypothesis is that the most affected basal epithelial cells die and fail to transition into functional wing cells. These damaged cells eventually undergo apoptosis and become pyknotic. They are extruded from the epithelium, and in that process, they appear microcyst-like on examination. The superficial corneal surface is secondarily affected both by these anatomic abnormalities and alterations in superficial corneal cell replenishment and tear film stability.

The current management guidelines for belantamab mafodotin-related corneal events include the use of preservative-free lubricant eye drops, dose reductions, and dose delays. The efficacy of steroid eye drops was systematically evaluated in a randomized ocular substudy in the DREAMM-2 study, and the results revealed that empiric topical corticosteroid therapy conferred no benefit. Corneal histopathologic samples in participants treated with belantamab mafodotin with this epitheliopathy are lacking. A more complete understanding of the pathophysiology of the corneal events seen in these participants could help confirm current hypotheses and inform management of these AEs. To do this, impression cytology or SK will be employed in this study to collect corneal epithelium with deposits for analysis. Advice from a council of corneal ophthalmology experts has been sought, and it is recommended that a total of 5 samples with sufficient

material for examination will provide confirmatory diagnosis of the underlying pathology and composition of these deposits. At least one highly experienced ophthalmic pathologist and laboratory will be utilized for tissue analysis.

4.3. End of Study Definition

The end of the study is defined as the date of the last visit of the last participant in the study or last scheduled procedure shown in the SoA for the last participant in the trial.

A participant is considered to have completed the study if he/she has completed all phases of the study including the last visit, as specified in the SoA.

5. STUDY POPULATION

5.1. Inclusion Criteria

Participants are eligible to be included in the study only if all the following criteria apply:

1. Male or female, aged 18 years or older (at the time consent is obtained).
2. Capable of providing signed written informed consent, which includes compliance with the requirements and restrictions listed on the consent form.
3. Participants with RRMM who have received or are currently receiving treatment with belantamab mafodotin AND diagnosed with MECs on slit-lamp examination or confocal microscopy, with or without symptoms, in at least one eye.
 - a. If patient only had superficial punctate keratopathy with no evidence of MEC's they are not eligible.
4. If undergoing SK procedure, treating provider has determined there is no excessive risk to the participant (see Section [6.2](#)).

5.2. Exclusion Criteria

Participants are excluded from the study if any of the following criteria apply:

1. Any serious and or/unstable medical or psychiatric disorder, or other conditions that could interfere with the participant's safety.
2. Any excess risk of delayed wound healing (e.g., diabetes mellitus).
3. Do not meet criteria specified by the study or program through which they would receive belantamab mafodotin.
4. Any patient taking concurrent medication that may affect the cornea (i.e. amiodarone, some chloroquines).
5. Any patient with decreased corneal sensation.
6. Eye infections, including infectious keratopathy, stye, blepharitis, and conjunctivitis.
7. An active uveitis including anterior, posterior, or panuveitis in either eye.
8. Permanent legal blindness in the fellow (non-study) eye.

Note: If the participant's eyes are equally affected with the MECs, the study eye will be the one with lesser visual acuity.

6. STUDY INTERVENTION(S) AND CONCOMITANT THERAPY

6.1. Study Intervention(s) Administered

Impression cytology is a technique used to collect superficial layers from the ocular surface through the application of cellulose acetate filter paper. The procedure is performed with or without topical anesthesia by an ophthalmologist or ocular pathologist.

SK is a method to remove a small region of the corneal epithelium down to but not including the level of the Bowman's membrane. This procedure will be performed by an ophthalmologist and will be conducted in the eye clinic or hospital under local anesthesia with appropriate antisepsis.

In this study, impression cytology or SK will be employed to collect corneal epithelium with epithelial changes for analysis.

6.2. Patient Selection Considerations

6.2.1. Selection of Right or Left eye for the procedure

The study eye will be the one that appears to have a greater number of MECs. If both eyes appear equal in terms of epithelial changes, the eye with the worse visual acuity will be selected; if both eyes have the same visual acuity, then the investigator can select either eye.

6.2.2. Selection of SK or IC procedure

The following guidance should be considered before deciding which procedure (IC or SK) to perform:

- 1) Patients should be assessed carefully for participation in either procedure. Patient eligibility factors to be considered include but are not limited to: excessive risk of delayed wound healing, history of concerning ocular or systemic infections, ocular condition that may place the patient at increased risk for recovery, social or medical circumstances that would make the risk of increased recovery time too high
- 2) Corneal sensation is checked at the screening visit for this study, and any eyes with reduced sensation should be considered ineligible for SK.
- 3) For SK, a higher keratopathy disease burden, greater predominance of MECs and central corneal location of MECs is preferred.

6.3. Impression Cytology Procedure

The study eye will be selected using the criteria described above. Following topical anesthesia, an eyelid speculum, will be placed. Next, the filter paper will be pressed to a preidentified region on the corneal surface of the study eye with a glass rod (or similar instrument) for 5–10 seconds. The filter papers obtained from the procedure will contain epithelial layers from areas of the cornea with microcyst-like changes and will be analyzed through histologic techniques. The filter paper will be placed on a glass slide and cover slip placed on top. The eye speculum will be removed and a topical antibiotic drop (e.g. polytrim) will be prescribed for 4 times a day for 7 days.

6.4. Superficial Keratectomy Procedure

The study eye will be selected using the criteria described above. Following topical anesthesia (such as proparacaine hydrochloride 0.5%) and a drop of povidone iodine 5% for antisepsis, an eyelid speculum will placed. The eye will then be visualized using a slit-lamp or operating microscope in a procedure room. The corneal epithelium of interest (the region that contains the MECs) will be carefully removed using either a Weck-Cel/dry cellulose sponge or small blade; Jeweler or 0.12 forceps may be required in some cases. The tissue will be submitted in formalin for histologic analysis. Care should be taken to minimize crush artefact to the epithelium and to avoid damage to Bowman layer.

Post procedure, another drop of povidone iodine 5% will be placed, followed by a drop of balanced salt solution or topical anesthetic (to wash out any residual povidone-iodine). A bandage contact lens will be placed.

[figure not shown]
It is recommended that a topical antibiotic and a topical steroid (or a fixed combination of both) is prescribed 4 times per day, each, for at least one week (or longer), until the epithelial defect is documented as healed and the bandage contact lens is no longer required in the assessment of treating Ophthalmologist. The topical antibiotic may be discontinued once the epithelial defect has healed. The topical steroid should be tapered off over the following two weeks.

The expected time for corneal re-epithelialization is 7–10 days [Ashby, 2014]. The procedure can cause some pain to the participant but is generally safe and well tolerated. Pain, if any, can be managed by the use of artificial tears. A bandage contact lens should be helpful in reducing the need for pain medication. In participants with symptomatic blurred vision, the procedure may result in temporary visual improvement. The procedure may also be complicated by an infection or worsening vision. An ocular pathologist will be consulted to determine the appropriate testing of tissue sample.

[figure not shown]
If the epithelial defect has not healed completely at the day 7 visit, the bandage contact lens should be left in place and both the steroid and antibiotic continued. The participant should be examined again in approximately 1 week.

The participant should be re-examined 2 weeks after the SK procedure if the epithelial defect does not heal completely in the first follow-up. Otherwise, this follow-up is not required. In the event the cornea has not healed at 2 weeks, additional follow-up should be conducted at the ophthalmologist's discretion until healing is confirmed.

CCI

CCI

6.8. sBCMA Sample Collection and Analysis

The BCMA receptor undergoes gamma-secretase mediated cleavage, leading to release of the BCMA extracellular domain as soluble BCMA (sBCMA) into the circulation [Laurent, 2015].

Samples will be collected to measure concentrations of sBCMA at a single timepoint, prior to IC or SK procedure. Serum analysis for sBCMA will be performed under control of GSK (further details are included in the SRM). Raw data will be archived at the bioanalytical site (detailed in the SRM).

The actual date and time of each blood sample collection will be recorded. Details on sBCMA blood sample collection including blood volumes, processing, storage, and shipping procedures are provided in the SRM.

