1.2. Schema

1.3. Schedule of Activities (SoA)

Procedure	Screening	Pre-IC or SK procedure	IC or SK procedure (day of procedure)	Post-IC or SK procedure ^e	Safety follow-up (up to 1 week after SK procedure)	Safety follow-up (2 weeks after SK procedure) ^f	Additional follow-up at ophthalmologist's discretion ^g
Informed consent	X						
Eligibility criteria	X						
Slit-lamp examination and confocal microscopy (if available) ^a with imaging		X			X ^d		
Snellen eye test ^a			X		X	X	
CCI							
Corneal tissue sampling ^c			X				
Pathology review of corneal sample				X			
Ophthalmology post-procedure checkup							X
Vital signs (pulse and blood pressure)			X				
AEs/SAEs			X	X	X	X	
Data Collection ^b	X	X	X	X	X	X	X
CCI							
Blood Collection ^j			X				

AE, adverse event; CCI

IC, impression cytology; SAE, serious adverse event; SK, superficial keratectomy.

^aAn ophthalmic examination that includes best-corrected visual acuity, slit-lamp examination, and confocal microscopy (if available) must be performed prior to the impression cytology or keratectomy procedure to document site and size of corneal epithelial changes and to correlate imaging with pathologic findings. The slit-lamp examination must include orbit/lid/adnexa, conjunctiva, sclera, cornea, anterior chamber, iris, lens, and anterior vitreous. Confirmatory anterior segment photography is also required unless acceptable corneal images are available from an examination performed <14 days prior to impression cytology or SK. It is recommended that the imaging examination be performed at least 24 hrs prior to the procedure.

CCI

^cGSK may store samples for up to 3 years after the end of the study to achieve study objectives. Additionally, with participants' consent, samples may be used for further research by GSK or others such as universities or other companies to contribute to the understanding of the pathophysiology of belantamab mafodotin-associated keratopathy, the development of related or new treatments, or research methods.

^dPreferred timing for follow-up slit-lamp examination is 24–48 hours post SK procedure but must be performed within 1 week after SK procedure. Safety follow-up after impression cytology is not required unless the participant is experiencing discomfort or an AE.

^eThe AE/SAE followup immediately after the Post-IC or SK procedure can be done by phone, in the 24–48 hours post-procedure.

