^d Preferred timing for follow-up slit-lamp examination is 24–48 hours post SK procedure but must be performed within 1 week after SK procedure. Safety follow-up after impression cytology is not required unless the participant is experiencing discomfort or an AE.

^e The AE/SAE follow-up immediately after the Post-IC or SK procedure can be done by phone, in the 24–48 hours post-procedure.

^f The participant should be reexamined 2 weeks after the SK procedure if the epithelial defect does not heal completely in the first follow-up. Otherwise, this follow-up is not required.

^g In the event the cornea has not healed at 2 weeks, additional follow-up should be conducted at the ophthalmologist's discretion until healing is confirmed.

^h Minimal additional data will be collected to adequately characterize the development of the corneal epithelial changes in participating patients.

CCI

Document: \\ieedc-vnasc01\Biosdata\GSK\GSK2857916\UZA78766\Biostatistics\Documentation\SAP\UZA78766_214098_SAP_v2.0_12OCT2022.docx

Author: PPD

Version Number: 2.0

Version Date: 12OCT2022

Reference: CS_WI_BS005

[figure not shown]
Template No.: CS_TP_BS016 Revision 6

Effective Date: 02Dec2019

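### Protocol 6.4 sets the post-keratectomy healing check at day 7, but the Schedule of Activities prefers its only visible follow-up slit-lamp at 24–48 hours and leaves the first follow-up undated

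*Protocol*

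**What the plan says.** **Protocol 6.4.** The paragraph on delayed healing opens "If the epithelial defect has not healed completely at the day 7 visit" and then instructs that "the bandage contact lens should be left in place and both the steroid and antibiotic continued". It goes on: "The participant should be examined again in approximately 1 week". The next paragraph states the same trigger without a day: "The participant should be re-examined 2 weeks after the SK procedure if the epithelial defect does not heal completely in the first follow-up". The section also says "The expected time for corneal re-epithelialization is 7–10 days". It recommends antibiotic and steroid drops for a week or more, until healing is documented and the ophthalmologist judges that the lens can go.

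**SoA (Protocol 1.3 and SAP 3.2).** The visible grid has one first-week follow-up column, running up to 1 week after SK. It is the only post-procedure column in which a slit-lamp examination is marked. Footnote d reads, in both documents, "Preferred timing for follow-up slit-lamp examination is 24–48 hours post SK procedure but must be performed within 1 week after SK procedure". The separate post-procedure column carries pathology review, adverse events and data collection, with no eye examination in its visible rows. Under footnote e its adverse-event contact "can be done by phone, in the 24–48 hours post-procedure". Footnote f makes the 2-week visit conditional on an unhealed defect at the first follow-up and gives no date for that follow-up. Footnote g leaves anything after 2 weeks to the ophthalmologist.

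In the readable text of both documents, a day 7 visit is named only in Protocol 6.4.

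**The concern.** Section 6.4 puts the healing decision at one week, when healing is expected. The SoA steers the same examination to the first or second day, before Section 6.4 expects most eyes to have closed. Footnote f then lets that early look count as the first follow-up. Protocol Section 8 requires adherence to the design, the SoA included, so both texts apply. A site scheduling from the SoA alone would not see day 7.

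What could be lost is one examination of an eye with an open defect under a bandage lens and a topical steroid. The protocol names infection and worsening vision as possible complications of SK (6.4), and it lists close monitoring among its risk controls (2.3.2).

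Eyes that heal on time are affected too. If an eye closes by day 7 but is next examined at 2 weeks, the lens and full-frequency drops could continue for up to 14 − 7 = 7 days longer than a day 7 check would have required.

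**Working it through.** The plan states no figure for the interval between examinations, so there is nothing to reproduce. The check is a comparison of texts and a count of days after SK.

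**Inputs**
- Healing check: day 7; next examination about 1 week later (Protocol 6.4).
- First-week slit-lamp: preferred on days 1–2, latest day 7 (footnote d).
- Next scheduled visit: day 14, if unhealed at the first follow-up (footnote f).
- Healing time: 7–10 days (6.4). Section 2.3 anticipates healing within 7 days and says that a 3–4 mm central defect typically heals in 2 days.
- Visits: up to 6 for SK (4.1).
- Enrolment: stops at 5 evaluable SK samples, with a cap of 25 participants (4.1).

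**1. Which visit is the first follow-up?** Section 6.4 gives day 7 plus about 7 days, so 7 + 7 = 14. That is the 2-week visit which the next paragraph ties to the first follow-up. Within 6.4, the first follow-up is therefore day 7.

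**2. Slit-lamp at the preferred time, with no other first-week examination.** Gap to the 2-week visit: 14 − 2 = 12 to 14 − 1 = 13 days.

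**3. Slit-lamp at day 7, which footnote d permits.** Gap: 14 − 7 = 7 days, in agreement with 6.4.

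**4. Both examinations.** The gaps are 7 − 2 = 5 to 7 − 1 = 6 days, then 14 − 7 = 7 days. The longest is 7 days, which is 12 − 7 = 5 to 13 − 7 = 6 days shorter than in step 2.

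**5. Position relative to healing.** The preferred examination falls 7 − 2 = 5 to 7 − 1 = 6 days before the end of Section 2.3's 7 days. It falls 7 − 2 = 5 to 10 − 1 = 9 days before healing on Section 6.4's figures. All of days 7–10 lies inside the step 2 gap.

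**6. Who is affected.** Only SK participants unhealed at 24–48 hours, at sites that hold no day 7 visit. The documents give no rate for either condition. The range is none to all SK participants: 0–5 if every SK sample is evaluable and enrolment stops at 5, and never more than 25.

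**The case against.** The strongest reply is that the texts do not conflict. Day 7 lies inside footnote d's mandatory one-week limit, and a stated preference does not cancel Section 6.4. The ophthalmologist performing SK will be working from 6.4, where day 7 is written, and step 1 shows that the intended first follow-up can be worked out. This stands. The problem arises only when the preferred time becomes the sole first-week examination.

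Nor is that sole examination a certainty. Footnote d times the slit-lamp cell, not the whole visit, and the post-procedure contact may be by phone but need not be. Continuing drops until healing is documented also points to a check at about one week or later. This stands in part: it makes a later look likely, but it sets no date.

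Other safeguards lower the exposure. Patients at excess risk of delayed healing are excluded (5.2), and extra visits are allowed when healing is slow (4.1). Those visits are permitted rather than scheduled, and footnote g's discretionary follow-up starts only after 2 weeks.

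Finally, some SoA rows and footnotes are redacted and the study schema is not shown. A day 7 visit could appear there.

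A reader might infer that following the SoA breaches Section 6.4, or that unhealed eyes drop out of care. Neither is supported. One day 7 visit meets both texts. An eye found unhealed goes on to the 2-week visit, and after that, "In the event the cornea has not healed at 2 weeks, additional follow-up should be conducted". A reader might also take the blank slit-lamp cell at 2 weeks to mean that no eye examination is planned then. Re-examination of the defect already implies one.

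**Conclusion.** The point holds as a minor patient-safety inconsistency. At the SoA's preferred timing, with no other first-week examination, an unhealed eye has no scheduled examination for 12–13 days, against at most 7 days on the schedule in Section 6.4.

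That interval is conditional. It assumes an eye unhealed at 24–48 hours, no day 7 visit, no discretionary visit, and nothing contrary in the redacted rows or the schema. How often these coincide cannot be estimated from the documents.

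The result should not be read as a treatment error. For an eye that is simply unhealed, the day 7 instruction is to leave the lens and continue both drugs, so what is missed is the look itself. The primary pathology endpoint is unaffected, because the tissue is taken at the procedure.

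**What to change.** Amend SoA footnotes d and f in Protocol 1.3, and the copy in SAP 3.2, to say three things:
- The first follow-up healing check, which decides whether the 2-week visit is needed, is a slit-lamp examination at day 7.
- It may be omitted if healing was already documented at an earlier examination.
- The 24–48 hour slit-lamp remains as a preferred additional early check.

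**Cost.** A protocol amendment, with the ethics committee approval that Section 10.1.1 requires, and matching SAP text. For participants, it means at most one extra brief visit, and only for those seen at 24–48 hours and not yet healed. The count can stay at Section 4.1's 6 SK visits if the early examination also serves as the adverse-event contact: screening, pre-procedure, procedure, 24–48 hours, day 7, 2 weeks. The synopsis gives 5 visits and should be aligned at the same time.

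SAP 17.1 tabulates only the latest non-missing value when there are two safety follow-up visits. An early examination recorded as one of them could therefore drop out of the by-visit tables, although it would stay in the listings.

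A healed yes/no item and a slit-lamp mark in the 2-week column would be useful clarifications. They are optional and not part of the required change.
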